5.3 Flowchart of the study cohort assembly

For rivaroxaban vs. warfarin

	Optum		Truven		Medicare	
	Less Excluded Patients	Remaining Patients	Less Excluded Patients	Remaining Patients	Less Excluded Patients	Remaining Patients
All patients		75,894,642		200,203,908		6,886,908
Did not meet cohort entry criteria	-74,960,282	934,360	-199,073,812	1,130,096	-2,028,461	4,858,447
Excluded due to insufficient enrollment	-92,301	842,059	-95,091	1,035,005	-1,551,114	3,307,333

Excluded due to prior use of referent	-482,398	359,661	-622,538	412,467	-2,080,069	1,227,264
Excluded due to prior use of exposure	-205,565	154,096	-204,425	208,042	-660,796	566,468
Excluded because patient qualified in >1 exposure category	-7	154,089	-26	208,016	-81	566,387
Excluded based on Age	-624	153,465	0	208,016	-155	566,232
Excluded based on Gender	0	153,465	0	208,016	0	566,232
Excluded based on Inclusion #1 - Age >=18	-86	153,379	-264	207,752	-65	566,167
Excluded based on Inclusion #2 & 3 - Atrial fibrillation	-83,438	69,941	-129,172	78,580	-348,521	217,646
Excluded based on Inclusion #4	-13,297	56,644	-16,046	62,534	-36,136	181,510
Excluded based on Exclusion #1a - Mitral stenosis	-275	56,369	-154	62,380	-399	181,111
Excluded based on Exclusion #1b - Prosthetic heart valve	-1,238	55,131	-789	61,591	-3,016	178,095
Excluded based on Exclusion #1e - atrial myxoma or left ventricular thrombus	-158	54,973	-35	61,556	-234	177,861
Excluded based on Exclusion #1f - Active infective endocarditis	-279	54,694	-138	61,418	-401	177,460
Excluded based on Exclusion #2a - Active bleeding or bleeding history	-3,413	51,281	-2,716	58,702	-8,256	169,204
Excluded based on Exclusion #2b.1 - Major Surgery	-1,564	49,717	-1,561	57,141	-6,484	162,720
Excluded based on Exclusion #2b.2 - Bleeding diathesis	-1,235	48,482	-885	56,256	-3,832	158,888
Excluded based on Exclusion #2b.3 - Intracranial neoplasm, AV malformation, cerebral aneurysm	-259	48,223	-283	55,973	-422	158,466
Excluded based on Exclusion #2d - Thrombocytopenia	0	48,223	0	55,973	0	158,466
Excluded based on Exclusion #2e - Uncontrolled hypertension	-47	48,176	-105	55,868	-300	158,166
Excluded based on Exclusion #3a.1 - stroke plus disabling stroke effects	-257	47,919	-152	55,716	-847	157,319
Excluded based on Exclusion # 3a.2 - stroke	-103	47,816	-88	55,628	-642	156,677
Excluded based on Exclusion #3b - TIA	-17	47,799	-25	55,603	-123	156,554
Excluded based on Exclusion #3c - DVT & PE	-1,095	46,704	-853	54,750	-3,185	153,369

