3	Non-valvular Atrial fibrillation Subjects with newly diagnosed atrial fibrillation are eligible provided that: - there is evidence that the atrial fibrillation is non-valvular - cardioversion is not planned - there is ECG evidence on 2 occasions 24 hours apart demonstrating atrial fibrillation			
	For Inclusion Criteria 4 It is either A) History of ischemic stroke or TIA or arterial embolism -OR- B) 2 of the following 4 1) Heart failure 2) Hypertension 3) Age >=75 4) Diabetes			
4	History of prior ischemic stroke, TIA or non-CNS systemic embolism believed to be cardioembolic in origin	Measured any time prior to and including day of drug initiation in any diagnosis position and inpatient or outpatient care setting: Ischemic stroke: ICD-9 diagnosis: 433.x, 434. x, 436.xx TIA: ICD-9 diagnosis: 435.xx Systemic embolism: ICD-9 diagnosis: 444.xx	
Patorno, Elisabetta et al. "Cardiovascular outcomes associated with canagliflozin versus other non-gliflozin antidiabetic drugs: population based cohort study." BMJ 2018;360:k119 http://dx.doi.org/10.1136/bmj.k119
 
Patorno, Elisabetta et al. "Empagliflozin and the Risk of Heart Failure Hospitalization in Routine Clinical Care: A First Analysis from the Empagliflozin Comparative Effectiveness and Safety (EMPRISE) Study." Circulation. 2019 Apr 8. doi: 10.1161/CIRCULATIONAHA.118.039177
	
	OR 2 or more of the following risk factors	Measured anytime prior to and including day of drug initiation in any diagnosis position and inpatient or outpatient care setting:		
4a	– Heart failure and/or left ventricular ejection fraction ≤35%	Heart failure: ICD-9 diagnosis: 428.x, 398.91, 402.01, 402.11, 402.91, 404.01, 404.11, 404.91, 404.03, 404.13, 404.93	
Patorno, Elisabetta et al. "Cardiovascular outcomes associated with canagliflozin versus other non-gliflozin antidiabetic drugs: population based cohort study." BMJ 2018;360:k119 http://dx.doi.org/10.1136/bmj.k119
 
Patorno, Elisabetta et al. "Empagliflozin and the Risk of Heart Failure Hospitalization in Routine Clinical Care: A First Analysis from the Empagliflozin Comparative Effectiveness and Safety (EMPRISE) Study." Circulation. 2019 Apr 8. doi: 10.1161/CIRCULATIONAHA.118.039177
	

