Appendix A

4b	
– Hypertension (defined as use of antihypertensive medications within 6 months before the screening visit or persistent systolic blood pressure above 140 mmHg or diastolic blood pressure above 90 mmHg)
	
Measured 180 days prior to and including day of drug initiation in any diagnosis position and inpatient or outpatient care setting:
 
Hypertension: ICD-9 diagnosis: 401.x – 405.x
 
Plus following medication use within 6 months: Refer to the 'Hypertension meds' sheet for list of medications
	
Patorno, Elisabetta et al. "Cardiovascular outcomes associated with canagliflozin versus other non-gliflozin antidiabetic drugs: population based cohort study." BMJ 2018;360:k119 http://dx.doi.org/10.1136/bmj.k119
 
Patorno, Elisabetta et al. "Empagliflozin and the Risk of Heart Failure Hospitalization in Routine Clinical Care: A First Analysis from the Empagliflozin Comparative Effectiveness and Safety (EMPRISE) Study." Circulation. 2019 Apr 8. doi: 10.1161/CIRCULATIONAHA.118.039177

4c	– Age ≥75 years	
Measured at the time of drug initiation: Age ≥75 years
	
4d	
– Diabetes mellitus (defined as a history of type 1 or type 2 diabetes mellitus or use of antidiabetic medications within 6 months before screening visit)
	
Measured any time prior to and including day of drug initiation in diagnosis position and inpatient or outpatient care setting:
 
DM type 2: ICD-9 diagnosis: 250.x0 or 250.x2 ICD-10 diagnosis: E11.x
 
DM type 1: ICD-9 diagnosis: 250.x1 or 250.x3 ICD-10 diagnosis: E10.x
 
-OR-
 
Following drug dispensing within 6 months of drug initiation: Refer to the 'Diabetes meds' sheet for list of DM Drugs
	
Patorno, Elisabetta et al. "Cardiovascular outcomes associated with canagliflozin versus other non-gliflozin antidiabetic drugs: population based cohort study." BMJ 2018;360:k119 http://dx.doi.org/10.1136/bmj.k119
 
Patorno, Elisabetta et al. "Empagliflozin and the Risk of Heart Failure Hospitalization in Routine Clinical Care: A First Analysis from the Empagliflozin Comparative Effectiveness and Safety (EMPRISE) Study." Circulation. 2019 Apr 8. doi: 10.1161/CIRCULATIONAHA.118.039177

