2e	Sustained uncontrolled hypertension: systolic blood pressure \geq 180 mmHg or diastolic blood pressure \geq 100 mmHg	
Measured 180 days prior to and including day of drug initiation in any diagnosis position and Inpatient care or ED setting:
 
Malignant hypertension: ICD-9 diagnosis: 401.0x Hypertensive urgency/Hypertensive crisis: ICD-10 diagnosis: I16.x
	
3	Concomitant Conditions and Therapies		
3a	Severe, disabling stroke (modified Rankin score of 4 to 5, inclusive) within 3 months or any stroke within 14 days before the randomization visit	
1) Measured 90 days prior to and including day of drug initiation in position and care setting specified below:
 
Stroke(primary diagnosis position, inpatient care setting): ICD-9 diagnosis: 430.xx, 431.xx, 433.xx, 434.xx, 436.xx,
 
-PLUS-
 
Disabling stroke effects (any position, any care setting, with 7-83 days between the strokes) ICD-9 diagnosis: 438.xx Late effects of cerebrovascular disease ICD-10 diagnosis: I69.xx Sequela of cerebrovascular disease (hemiplegia etc); Z73.6x Limitation of activities due to disability
 
2) Measured 14 days prior to and including day of drug initiation in primary diagnosis position and inpatient care setting:
 
Stroke: ICD-9 diagnosis: 430.xx, 431.xx, 433.xx, 434.xx, 436.xx
	
Patorno, Elisabetta et al. "Cardiovascular outcomes associated with canagliflozin versus other non-gliflozin antidiabetic drugs: population based cohort study." BMJ 2018;360:k119 http://dx.doi.org/10.1136/bmj.k119
 
Patorno, Elisabetta et al. "Empagliflozin and the Risk of Heart Failure Hospitalization in Routine Clinical Care: A First Analysis from the Empagliflozin Comparative Effectiveness and Safety (EMPRISE) Study." Circulation. 2019 Apr 8. doi: 10.1161/CIRCULATIONAHA.118.039177

3b	Transient ischemic attack within 3 days before the randomization visit	
Measured 3 days prior to and including day of drug initiation in primary diagnosis position and inpatient care or ED setting:
 
TIA: ICD-9 diagnosis: 435.xx
	

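### For ICD-9 records, exclusion 2e searches 401.0x alone although the plan treats 401.x–405.x as hypertension, so it can miss malignant hypertension coded in the other four families

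*Combined protocol and SAP*

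**What the plan says.** Appendix A, exclusion 2e, sets out the trial's rule, which begins "Sustained uncontrolled hypertension: systolic blood pressure" and gives blood-pressure thresholds. The claims version looks back 180 days, in "any diagnosis position and Inpatient care or ED setting". It has two code lines. Under a malignant hypertension label it gives "ICD-9 diagnosis: 401.0x". Under a hypertensive urgency or crisis label it gives "ICD-10 diagnosis: I16.x". No other ICD-9 code is in the row, and no reason is given for stopping at 401.

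Two inclusion rows in the same appendix use a wider set of ICD-9 families. Inclusion 4b (hypertension) uses "ICD-9 diagnosis: 401.x – 405.x" together with an antihypertensive drug. Inclusion 4a (heart failure) uses "428.x, 398.91, 402.01, 402.11, 402.91, 404.01, 404.11, 404.91, 404.03, 404.13, 404.93".

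Section 5.3 reports the effect in the row "Excluded based on Exclusion #2e - Uncontrolled hypertension": 47 patients removed in Optum, 105 in Truven and 300 in Medicare. Section 5.2.2 says that the trial's criteria were followed as closely as possible.

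Appendix B also tabulates a covariate named malignant hypertension, before and after matching. Neither appendix gives its codes, care setting or look-back.

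**The concern.** The plan recognises five ICD-9 families as hypertension when it lets patients in, but searches only one of them for the severe form when it keeps patients out. The families left out of 2e are those used when hypertension is linked to heart disease, kidney disease or a secondary cause. If malignant hypertension is recorded there, 2e does not see it, and the patients retained would tend to be those with organ disease.

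What is at stake is likeness to the trial population. The primary composite includes hemorrhagic stroke and the control outcome is major bleeding. Severe hypertension is relevant to both, so the exclusion should do what its label says.

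**Working it through.** **Inputs.** Code lists: Appendix A, rows 2e, 4a, 4b and 3l. Patient flow: section 5.3. Matched numbers, risk and power: sections 9 and 10. Covariates: Appendix B.

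**1. Which codes 2e reaches.**

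| Row | Purpose | ICD-9 hypertension codes |
|---|---|---|
| 4b | counts as hypertension | 401.x to 405.x |
| 4a | counts as heart failure | 402.01, 402.11, 402.91, 404.01, 404.11, 404.91, 404.03, 404.13, 404.93 |
| 2e | excludes | 401.0x |

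The documents attach the word malignant only to 401.0x. That 402.0x to 405.0x are also malignant forms is taken here from the ICD-9 classification. Row 4a fits this: its codes run in sets whose fourth digit is 0, 1 or 9, and 401.0x has the digit 0. The sponsor can confirm it from the code book.

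Appendix A says that ICD-10 lists are shortened for space and that the full lists are in a linked folder. It says nothing of the kind about ICD-9 lists. The folder is not part of the documents.

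**2. The plan's own flow figures, reproduced.**
- Optum: 48,223 − 47 = 48,176 (0.10% removed)
- Truven: 55,973 − 105 = 55,868 (0.19%)
- Medicare: 158,466 − 300 = 158,166 (0.19%)
- Total: 452 / 262,662 = 0.17%

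**3. Plausible size of the gap.** The documents give no count of 402.0x–405.0x. Assume that a share s of hospital- or ED-coded malignant hypertension carries only such a code. Patients missed per patient caught = s / (1 − s).
- s = 0.15: 0.15 / 0.85 = 0.18, so about 80 missed (452 × 0.15 / 0.85)
- s = 0.50: 0.50 / 0.50 = 1.0, so 452 missed

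The range for s is an assumption without a source. Within it, 452 is generous, because the 452 removed include patients caught by I16.x.

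Carried to the match at the upper end:
- Matched fraction: 102,636 / 223,668 = 0.459
- Matched patients: 452 × 0.459 ≈ 207
- Expected events at 10.08 per 1,000: 207 × 0.01008 ≈ 2.1, of 1,034.57 (0.2%)
- At five times the average risk: about 10 events (1%)

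The denominator 223,668 is the Appendix B unmatched total. The section 5.3 final cohort is 40,604 + 50,085 + 133,230 = 223,919, and the difference does not affect the result.

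**4. Balance between groups after matching (pooled).**
- Malignant hypertension: 15,342 (29.9%) against 15,479 (30.2%), standardised difference −0.01
- Heart failure: 32.7% against 32.6%, 0.00
- HAS-BLED mean: 3.47 against 3.47, 0.00

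**5. The covariate against the exclusion.** Unmatched patients carrying the covariate after all exclusions:
- Optum: (1,402 + 605) / (25,701 + 14,869) = 2,007 / 40,570 = 4.9%
- MarketScan: (14,434 + 7,875) / (32,295 + 17,748) = 22,309 / 50,043 = 44.6%
- Medicare: (24,773 + 11,920) / (92,403 + 40,652) = 36,693 / 133,055 = 27.6%
- Total: 61,009 / 223,668 = 27.3%
- Matched: 30,821 / 102,636 = 30.0%

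The plan thus uses the term malignant hypertension for a condition that excluded 0.17% of patients and for one still present in 27.3%.

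**6. What the correction could cost in power.** With E events, power = Φ(√(E/4) × |ln HR| − 1.96). For E = 1,034.57 and HR 0.79 this gives 0.966, which is the figure in section 10. If 5% of matched patients and events were lost (an assumption), E = 982.84 and power = 0.959.

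**The case against.** The case against has four parts.

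- **The code meanings come from outside the documents.** This is true, and it is why the conclusion is conditional on them. What the documents do show is that 4b spans five families and the ICD-9 line of 2e spans one.
- **Patients with these codes may leave anyway.** This stands. Some will also carry 401.0x. A crisis coded I16.x is excluded whatever the accompanying heart or kidney disease. Exclusion 3l removes stage 4–5 kidney disease, dialysis and transplant (3,281 + 2,012 + 7,391 = 12,684 patients). It does not, however, reach forms linked to heart disease alone.
- **Any code is only a proxy for a blood-pressure threshold.** This also stands. Appendix A has a colour key for weak mappings, lost in the text available, so row 2e may already be flagged. A weak proxy is still better for being complete.
- **The numbers are small and the groups balanced.** This stands on what is shown.

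A reader might infer two stronger things. One is that codes such as 402.01 wrongly help a patient to qualify, because they count under both 4a and 4b (the latter with a drug). That is not a defect: the excluded code 401.0x also counts under 4b, and inclusion and exclusion are separate filters. Row 4a also looks back without limit while 2e looks back 180 days, so an old 402.01 may properly pass. The other is that the 27.3% carrying the covariate measures the patients missed. It cannot be read so, because its codes and setting are unknown; a wider code list or the inclusion of outpatient claims could produce such a figure.

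**Conclusion.** The point holds as a gap in one code list. In ICD-9 records, 2e does not remove malignant hypertension coded 402.0x–405.0x unless 401.0x or I16.x is also present or another exclusion applies. This rests on the ICD-9 meaning of those codes.

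The number affected is not in the documents. It is probably small: of the order of 80 to 452 patients under the assumed range, and at most about 2 of 1,035 expected events at average risk. That estimate should be treated as provisional until the covariate is defined.

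A reader might infer that the gap biases the comparison. The documents do not support this: the related covariates are balanced after matching, and no difference between groups in the omitted codes is shown. Nor should the correction be taken to make the rule uniform across coding eras. I16.x is labelled urgency or crisis, a different concept from malignant hypertension, and adding ICD-9 codes does not change that. The gain is a cohort closer to the trial's exclusion.

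**What to change.** In Appendix A, exclusion 2e, extend the ICD-9 line to 401.0x, 402.0x, 403.0x, 404.0x and 405.0x, keeping the 180-day window and the inpatient or ED setting. If the four families were left out on purpose, give the reason in that row instead. Re-run the section 5.3 flowchart and the propensity-score match before any outcome analysis; the date under section 13 is still blank.

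State the codes, care setting and look-back of the Appendix B malignant hypertension covariate, explain the spread from 4.9% in Optum to 44.6% in MarketScan, and reconcile it with 2e.

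The cost is one edit to a code list, a re-run of cohort assembly and matching, a fresh balance and power review under sections 9 and 10, and a probably small loss of patients. Reporting how many patients the four added codes remove would settle the size of the gap.

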Appendix A

3c	Indication for anticoagulant therapy for a condition other than atrial fibrillation (e.g., VTE)	
Measured 180 days prior to and including day of drug initiation in any diagnosis position and inpatient or outpatient care setting:
 
1) Pulmonary embolism (PE): ICD-9 diagnosis: 415.xx ICD-10 diagnosis: I26.xx,
 
2) Deep vein thrombosis (DVT): ICD-9 diagnosis: 451.xx, 453.xx ICD-10 diagnosis: I26.xx, I80.xx, I81.xx, I82.xx, I26.xx
	
3d	
Treatment with:
 
 - Aspirin >100 mg daily - Aspirin in combination with thienopyridines within 5 days before randomization - Intravenous antiplatelets within 5 days before randomization - Fibrinolitics within 10 days before randomization - Note: Aspirin ≤100 mg monotherapy is allowed and thienopyridine monotherapy is allowed. 	
Measured 180 days prior to and including day of drug initiation: Aspirin dose >100mg: (Only prescription use is captured.)
 
Measured 10 days prior to and including day of drug initiation: Fibrinolytic agents: Alteplase, reteplase, tenecteplase, streptokinase, urokinase
 
Measured 5 days prior to and including day of drug initiation: Aspirin (any dose) + thienopyridines (clopidogrel or prasugrel or ticlopidine):
 
Measured 5 days prior to and including day of drug initiation: Cangrelor:
	
3e	Anticipated need for chronic treatment with a non-steroidal anti-inflammatory drug		
3f	Systemic treatment with a strong inhibitor of cytochrome P450 3A4, such as ketoconazole or protease inhibitors, within 4 days before randomization, or planned treatment during the time period of the study	
Measured 4 days prior to and including day of drug initiation as a dispensing of the following:
 
CYP inhibitors (selected): ketoconazole, metronidazole, amiodarone, cimetidine, omeprazole, fluoxetine, indinavir, ritonavir
	
3g	Treatment with a strong inducer of cytochrome P450 3A4, such as rifampin/rifampicin, within 4 days before randomization, or planned treatment during the time period of the study	
CYP inducers (selected): carbamazepine, phenytoin, rifampin/rifampicin, phenobarbital
	
3h	Anemia (hemoglobin <10 g/dL) at the screening visit	
Measured 180 days prior to and including day of drug initiation in any diagnosis position and inpatient or outpatient care setting:
 
Anemia (non-deficiency/neoplastic/chemotherapy/hemorrhagic associated): ICD-9 diagnosis: 282.x, 283.x, 284.x, 285.0, 285.2 (acute posthemorrhagic anemia), 285.22 (anemia of neoplastic disease), 285.3 (antineoplastic chemotherapy induced anemia) ICD-10 diagnosis: D55 - D62, D63.0
	
3i	Pregnancy or breast-feeding	
Measured 180 days prior to and including day of drug initiation in any diagnosis position and inpatient or outpatient care setting:
 
Refer to the 'Pregnancy' sheet.
	
3j	Any other contraindication to warfarin	N/A	
3k	Known HIV infection at time of screening	
Following diagnosis or drugs measured 180 days prior to and including day of drug initiation in any diagnosis position and inpatient or outpatient care setting:
 
HIV Infection: 042 Human immunodeficiency virus [HIV] disease 079.53 Human immunodeficiency virus, type 2 [HIV-2] V08 Asymptomatic human immunodeficiency virus [HIV] infection status -OR- Filled prescription for HIV treatment 180 days prior to drug initiation: Refer to the 'HIV treatment' sheet for list of treatments
	
Patorno, Elisabetta et al. "Cardiovascular outcomes associated with canagliflozin versus other non-glipizide antidiabetic drugs: population based cohort study." BMJ 2018;360:k119 http://dx.doi.org/10.1136/bmj.k119
 
Patorno, Elisabetta et al. "Empagliflozin and the Risk of Heart Failure Hospitalization in Routine Clinical Care: A First Analysis from the Empagliflozin Comparative Effectiveness and Safety (EMPRISE) Study." Circulation. 2019 Apr 8. doi: 10.1161/CIRCULATIONAHA.118.039177

Appendix A

3l	Calculated CLCR <30 mL/min at the screening visit (refer to Attachment 4 for calculating CLCR)	
Measured 180 days prior to and including day of drug initiation in any diagnosis position and inpatient or outpatient care setting:
 
CKD stage 4/5/ESRD: ICD-9 diagnosis: 585.4x, 585.5x, 585.6x ICD-10 diagnosis: N18.4x, N18.5x, N18.6x
 
-OR-
 
Dialysis/ Renal transplant: Refer to the 'Dialysis' sheet for list of codes

3m	Known significant liver disease (e.g., acute clinical hepatitis, chronic active hepatitis, cirrhosis), or ALT >3x the ULN	
Measured 180 days prior to and including day of drug initiation in any diagnosis/procedure position and inpatient or outpatient care setting:
 
Liver disease: ICD-9 diagnosis: 070.xx, 570.xx- 573.xx 456.0x-456.2x, 576.8x, 782.4x, 789.5x ICD-9 procedure: 39.1x, 42.91

4	Study Participation and Follow-up-Related Criteria	
4a	Serious concomitant illness associated with a life expectancy of less than 2 years	Measured 180 days prior to and including day of drug initiation:
4b	Drug addiction or alcohol abuse within 3 years before the randomization visit	
Measured 180 days prior to and including day of drug initiation in any diagnosis position and inpatient or outpatient care setting:
 
Alcohol abuse or dependence: 291.xx, 303.xx, 305.0x, 571.0x, 571.1x, 571.2x, 571.3x, 357.5x, 425.5x, E860.0x, V11.3x Drug abuse or dependence: 292.xx, 304.xx, 305.2x-305.9x, 648.3x

4c	Have received an experimental drug or used an experimental medical device within 30 days before the planned start of treatment	N/A
4d	Previous randomization in the present study or other study of rivaroxaban	N/A
4e	Known allergy or hypersensitivity to any component of rivaroxaban, warfarin or placebo excipients (includes lactose, microcrystalline cellulose, magnesium stearate, hypromellose, macrogol, croscarmellose sodium, sodium lauryl sulfate, titanium oxide/ferric oxide red, titanium dioxide/ferric oxide red, anhydrous lactose, pregelatinized starch, FD&C Red #6 barium lake, FD&C Yellow #10 aluminum lake, FD&C Blue #1 aluminum lake, FD&C Yellow #6 aluminum lake, cornstarch, lactose monohydrate)	N/A
4f	Inability or unwillingness to comply with study-related procedures	
Measured 180 days hospitalization prior to and including day of drug initiation in any diagnosis position and inpatient or outpatient care setting:
 
Non-compliance: ICD-9 diagnosis: V15.81 PERSONAL HISTORY OF NONCOMPLIANCE WITH MEDICAL TREATMENT PRESENTING HAZARDS TO HEALTH; V45.12 NONCOMPLIANCE WITH RENAL DIALYSIS

4g	Employees of the investigator or study center, with direct involvement in the proposed study or other studies under the direction of that investigator or study center, as well as family members of the employees or the investigator.	N/A

